1 PROTOCOL SUMMARY

1.1 Synopsis

Background and Rationale:

This study is designed to generate real-world data on dentin hypersensitivity (DH) sufferers among a general population. This study will aim to evaluate the impact of the use of a desensitizing toothpaste on oral health related quality of life. Data generated will provide real world information on the DH experience and how DH management treatment could impact oral health related quality of life.

Objectives and Endpoints:

Objective(s)	Endpoint(s)
Primary	
To describe subjects' oral health related quality of life over a 24 week period following the use of a sensitivity toothpaste containing 5% potassium nitrate, as measured by the Dentin Hypersensitivity Experience Questionnaire (DHEQ-48) in a population of DH sufferers.	Plot over time in DHEQ mean scores (0, 4, 8, 12, 16, 20 and 24 weeks): Section 1 - Impact on everyday life (Q1-3) Section 2 - Total Score (Q1-34) - Individual Domain scores O Restrictions (Q1-4), O Adaptation (Q5-16), O Social Impact (Q17-21), O Emotional Impact (Q22-29) O Identity (Q30-34) - Global oral health score (Q35) - Effect on life overall score (Q36-39)
To explore subjects' oral health related quality of life over a 24 week period following the use of a sensitivity toothpaste containing 5% potassium nitrate, as measured by the DHEQ-48 in further characterisation of DH sufferers by subgroups: Age group Diagnosis Use of sensitivity toothpaste Self-reported DH frequency	Plot over time in DHEQ mean scores (0, 4, 8, 12, 16, 20 and 24 weeks) for each subgroup: Section 1 - Impact on everyday life (Q1-3) Section 2 - Total Score (Q1-34) - Individual Domain scores O Restrictions (Q1-4), O Adaptation (Q5-16), O Social Impact (Q17-21), Emotional Impact (Q22-29)

Protocol Number: 216953

	o Identity (Q30-34)
	- Global oral health score (Q35)
	- Effect on life overall score (Q36-39)
To characterise subjects' change in oral health related quality of life over 24 weeks compared to baseline, following use of a sensitivity toothpaste containing 5% potassium nitrate, as measured by the DHEQ-48, in the overall population of DH sufferers and in 4 subgroups: Age group Diagnosis Use of sensitivity toothpaste Self-reported DH frequency	DHEQ Mean score over time compared to baseline (0, 4, 8, 12, 16, 20 and 24 weeks) to be analysed for overall population of DH sufferers and each sub-group: Section 1 - Impact on everyday life (Q1-3) Section 2 - Total Score (Q1-34, section 2) - Individual Domain scores (section 2) O Restrictions (Q1-4), O Adaptation (Q5-16), O Social Impact (Q17-21), Emotional Impact (Q22-29)
	. (000 04)
	,
	- Global oral health score (Q35) Effect on life everall score (Q36, 30)
The state of the PATTER And the state of the	- Effect on life overall score (Q36-39)
To identify the DHEQ domain items important to the overall population of DH sufferers following 24 weeks use of the sensitivity toothpaste	Percentage of DH sufferers who agree (score 5-7) to items in each respective domain at baseline and week 24
To explore the potential impact a sensitivity toothpaste containing 5% potassium nitrate	For overall population of DH sufferers and each sub-group:
has on subjects' reported pain in relation to DH in the overall population of DH sufferers and in 4 sub-groups: Age group Diagnosis	• Numeric Pain Rating Scale (NPRS) mean score over time compared to baseline (0, 4, 8, 12, 16, 20 and 24 weeks)
Diagnosis Use of sensitivity teethnests	• Plot over time in NPRS mean scores (0,
Use of sensitivity toothpaste Self-reported DH frequency	4, 8, 12, 16, 20 and 24 weeks)
	• Percentage of DH sufferers who achieve pain reduction identified as clinically important (pain reduction NPRS > 30%)
To explore subjects' overall satisfaction with DH treatment in the overall population of DH sufferers and in 4 sub-groups: Age group	At week 24, Satisfaction Numerical rating scale (NRS) mean scores for overall population of DH sufferers and each subgroup
Diagnosis Use of consitivity to the pasts	
Use of sensitivity toothpaste Self-reported DH frequency	

Protocol Number: 216953

To describe oral hygiene habits of DH	At baseline, summary of oral hygiene habits
sufferers according to oral hygiene	
questionnaire	

Study Design:

This will be a virtual, prospective, twenty-four weeks, open label study in subjects with DH (self-reported symptoms).

This study will aim to evaluate changes in oral health-related quality of life (OHrQoL) in subjects suffering from DH following the use of anti-sensitivity toothpaste for 24 weeks. Subjects' self-perception of DH will be evaluated by completion of a validated OHrQoL questionnaire (DHEQ-48) at baseline, 4, 8, 12, 16, 20 and 24 weeks.

Sufficient number of subjects (estimated 50% screen failure) aged between 18-65 years, who suffer from tooth sensitivity, will be screened to enroll approximately 650 to ensure 400 consumers complete the entire study (estimated 40%drop-out).

Subjects will be recruited through social media and other digital platforms. Subjects interested in the study will be sent to a landing page after clicking on an "Ad" or study link where they fill-out an initial pre-screening questionnaire and, if they are eligible, they will be sent an email with provided unique participant ID and the link to download the PPD app. After downloading the PPD app and logging in using a unique participant ID provided, they will review the electronic Inform Consent (eIC), they will be able to communicate with the PPD app's chat, via phone (study number linked to the study chat) or email. Subjects can use any or all of these methods as often as they need to until they are comfortable with their decision and may then accept or decline the eIC. No study-specific data collection will occur prior to subject consent. Subjects who do not actively access the study-specific website/app and provide consent will not have the possibility to contribute study data.

Once the subjects sign the eIC, they will complete a screening questionnaire which will aim to identify and exclude individuals whose sensitivity could be caused by other factors/clinical pathology for which dental healthcare professional advice should be sought. Subjects who qualify based on inclusion/exclusion criteria and the screening questionnaire will be enrolled and will be sent a desensitizing toothpaste (5% potassium nitrate). They will be asked to use it for 24 weeks, following the commercial tube instructions, recommended daily use and their normal oral healthcare habits, and to fill in the DHEQ form on 7 different occasions (Baseline (prior to any product use), 4, 8, 12, 16, 20 and 24 weeks).

At each DHEQ timepoint, subjects will receive reminders according to the schedule of activities.

Safety will be assessed by evaluation of AEs and will be collected remotely via an online, subject portal.

Study Products:

Sensodyne Fresh Mint Toothpaste (potassium nitrate 5%, sodium fluoride 0.15% w/v fluoride ion — CC USA marketplace toothpaste)

Protocol Number: 216953

Type and Planned Number of Subjects:

Sufficient number of subjects will be screened (estimated 50% screen failure) to enroll approximately 650 to ensure 400 evaluable subjects complete the entire study (estimated 40% drop out).

Statistical Analyses

For the primary objective, plots of the mean values for questions Q1-3 (section1) and for questions in section 2 total DHEQ score (sum Q1-34), each of the domain's mean values: Restrictions (sum Q1-4), Adaptation (sum Q5-16), Social Impact (sum Q17-21), Emotional Impact (sum Q22-29), Identity (sum Q30-34), Global oral health (Q35) and Effect on life overall (sum Q36-39) will be presented for the overall population of DH sufferers over 24 weeks to assess QoL over time, graphically.

The analyses for exploratory objectives are defined in the statistical section 12.4.3.

1.2 Schedule of Activities

The schedule of activities table provides an overview of the study.

Table 1-1 Schedule of Activities

Procedures	Screening	Baseline* Week 0 (Day 0)	Week 4 Day 28 (± 7 days)	Week 8 Day 56 (±7 days)	Week 12 Day 84 (±7 days)	16 Day 112	20 Day 140	Week 24 Day 168 (± 7 days)
Electronic Informed Consent	X							
Demographics	X							
Inclusion/exclusion criteria	X							
Screening questionnaire	X							
Subject eligibility	X							
Medical History ¹	X	X						
Concomitant Medications		X	X	X	X	X	X	X
DHEQ-48 completion		X	X	X	X	X	X	X
NPRS scale		X	X	X	X	X	X	X
Oral Hygiene questionnaire		X						
Study product shipped [dentifrice] ²		X						
Patients' satisfaction with treatment (NRS)								X
AEs ³	X	X	X	X	X	X	X	X
Study Conclusion								X

Abbreviations:

216953 | Protocol clinical protocol 08 Jul 2022 | TMF-194147 | 2.0

GSK Consumer Healthcare Clinical Protocol

Protocol Number: 216953

AEs: Adverse Events

DHEQ: Dentin Hypersensitivity Experience Questionnaire

NRS: Numerical Rating Scale NPRS: Numeric Pain Rating Scale

Footnotes

- ¹ Medical occurrences and AEs which subjects experience from the time of consent signature, but prior the use of the study product, will be recorded in the Medical History
- ² Product will be shipped only after baseline assessments have been completed
- ³ Any events experienced from the first use of the product until last administration of the study product will be recorded as AEs. All serious AEs (SAEs) will be collected immediately after a subject provides consent signature until last administration of the study product.
- * Baseline activities must be conducted within 14 days from subject eligibility

Protocol Number: 216953

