To characterise subjects' change in oral health related quality of life over 24 weeks compared to baseline, following use of a sensitivity toothpaste containing 5% potassium nitrate, as measured by the DHEQ-48, in the overall population of DH sufferers and in 4 subgroups: Age group Diagnosis Use of sensitivity toothpaste Self-reported DH frequency To identify the DHEQ domain items important to the overall population of DH sufferers following 24 weeks use of the sensitivity toothpaste	DHEQ Mean score over time compared to baseline (0, 4, 8, 12, 16, 20 and 24 weeks) to be analysed for overall population of DH sufferers and each sub-group: Section 1 - Impact on everyday life (Q1-3) Section 2 - Total Score (Q1-34, section 2) - Individual Domain scores (section 2) o Restrictions (Q1-4), o Adaptation (Q5-16), o Social Impact (Q17-21), o Emotional Impact (Q22-29) o Identity (Q30-34) - Global oral health score (Q35) - Effect on life overall score (Q36-39) Percentage of DH sufferers who agree (score 5-7) to items in each respective domain at baseline and week 24
To explore the potential impact a sensitivity toothpaste containing 5% potassium nitrate has on subjects' reported pain in relation to DH in the overall population of DH sufferers and in 4 sub-groups: Age group Diagnosis Use of sensitivity toothpaste Self-reported DH frequency	 For overall population of DH sufferers and each sub-group: Numeric Pain Rating Scale (NPRS) mean score over time compared to baseline (0, 4, 8, 12, 16, 20 and 24 weeks) Plot over time in NPRS mean scores (0, 4, 8, 12, 16, 20 and 24 weeks) Percentage of DH sufferers who achieve
To explore subjects' overall satisfaction with DH treatment in the overall population of DH sufferers and in 4 sub-groups: Age group Diagnosis Use of sensitivity toothpaste Self-reported DH frequency To describe oral hygiene habits of DH	pain reduction identified as clinically important (pain reduction NPRS > 30%) At week 24, Satisfaction Numerical rating scale (NRS) mean scores for overall population of DH sufferers and each subgroup At baseline, summary of oral hygiene habits
sufferers according to oral hygiene questionnaire	

Protocol Number: 216953

In this study is expected to observe a trend in favor of improvement in QoL over time after 24 week treatment period in a general population of DH sufferers, in particular the total DHEQ score.

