4 STUDY DESIGN

4.1 Overall Design

This will be a virtual, prospective, twenty-four weeks, open label study in subjects with DH (self-reported symptoms).

This study will aim to evaluate changes in oral health-related quality of life (OHrQoL) in subjects suffering from DH symptoms following the use of anti-sensitivity toothpaste for 24 weeks. Subjects' self-perception of DH will be evaluated by completion of a validated OHrQoL questionnaire (DHEQ-48) at baseline, 4, 8, 12, 16, 20 and 24 weeks.

Sufficient number of subjects (estimated 50% screen failure) aged between 18-65 years, who suffer from tooth sensitivity, will be screened to enroll approximately 650 to ensure 400 consumers complete the entire study (estimated 40% drop out).

Subjects will be recruited through social media and other digital platforms. Subjects interested in the study will be sent to a landing page after clicking on an "Ad" or study link where they fill-out an initial pre-screening questionnaire and if they are eligible, they will be sent an email with provided unique participant ID and the link to download the app. After downloading the and logging in using a unique participant ID provided, they will review the electronic Inform Consent (eIC), they will be able to communicate with the PPD virtual site team via the PPD app's chat, via phone (study number linked to the study chat) or email. Subjects can use any or all of these methods as often as they need to until they are comfortable with their decision and may accept or decline the eIC. No study-specific data collection will occur prior to subject consent. Subjects who do not actively access the study-specific website/app and provide consent will not have the possibility to contribute study data.

Once the subjects accept/sign the eIC, they will be able to fill-out a screening questionnaire which will aim to identify and exclude individuals whose sensitivity could be caused by other factors/clinical pathology for which dental healthcare professional advice should be sought. Subjects who qualify based on inclusion/exclusion criteria and the screening questionnaire will be enrolled and will be sent a desensitizing toothpaste (5% potassium nitrate). They will be asked to use it for 24 weeks, following the commercial tube instructions, recommended daily use and their normal oral healthcare habits, and to fill in DHEQ form on 7 different occasions (Baseline (prior to any product use), 4, 8, 12, 16, 20 and 24 weeks).

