4.4 Duration of Study Definition

The duration of the study is defined for each subject as the date that the signed eIC is provided through the end of the study follow-up period (168 days [+ 7days] post-baseline), subject death, early withdrawal from the study, lost to follow-up or overall study termination.

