8.1.3 Medical History and Medications

Details of relevant medical and surgical history, including allergies or drug sensitivity, will be collected in the eCRF (PPD app).

Medical occurrences and AEs which subjects experience from the time of consent signature, but prior the use of the study product, will be recorded in the Medical History section of the eCRF (PPD portal).

Medications/treatments, including prescription and non-prescription drugs, dietary supplements and herbal remedies, and recent vaccines taken from signing the ICF will be documented as concomitant medication/treatments in the eCRF (PPD app).

Details of any medications used by the subjects throughout the study will be collected in the eCRF (PPD app) with reason for use, unit dose, daily dose, and start and stop dates of administration.

8.2 Baseline Week 0

Baseline activities must be conducted within 14 days from subject eligibility and collected within PPD app:

- Medical History
- Medications
- DHEQ-48 questionnaire
- NPRS scale
- Oral hygiene questionnaire
- Product shipment (only after baseline assessments have been completed)
- Adverse events (AEs which subjects experience from the first use of the product until last administration of the study product, and SAEs)

8.3 Week 4, 8, 12, 16 and 20

The following data will be collected within PPD app:

- Concomitant Medications
- DHEO-48 questionnaire
- NPRS scale
- Adverse events

8.4 Week 24

The following data will be collected within PPD app:

Clinical Protocol

Protocol Number: 216953

- Concomitant Medications
- DHEQ-48 questionnaire
- NPRS scale
- Patients' satisfaction with treatment (NRS)
- Adverse events

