9.3.2 Patient satisfaction with treatment

The 11-item Numerical Rating Scale is an 11-point ordinal scale assessing satisfaction with the overall management of the condition for which the subjects sought help from treatment, from 0 (completely dissatisfied) to 10 (completely satisfied). Higher scores depict higher satisfaction (van Berckel *et al*, 2017).

Protocol Number: 216953

Subjects will be asked to indicate the numeric value on the segmented scale that best describes their satisfaction with the treatment after 24 weeks of use.

Subjects will be also asked to record comments on their satisfaction with treatment (e.g. Please give more details on why you are satisfied or dissatisfied with the product)

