### 3.3.3 Study Period

The duration of the study is defined for each subject as the date that the signed electronic informed consent (eIC) is provided through the end of the study follow-up period (168 days [+7days] post-baseline), subject death, early withdrawal from the study, lost to follow-up or overall study termination.

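### Does timing visits from baseline, when the toothpaste ships only afterwards, undermine the results reported as 24 weeks of use?

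*Protocol*

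**What the plan says.** **The clock.** Protocol 1.2 sets baseline at Day 0, Week 4 at Day 28 and Week 24 at Day 168, each follow-up visit with a window of 7 days either side. Protocol 4.4 runs each subject's participation to the "end of the study follow-up period (168 days [+ 7days] post-baseline", and SAP 3.3.3 says the same: "end of the study follow-up period (168 days [+7days] post-baseline".

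**The product.** The footnote in Protocol 1.2 ("Product will be shipped only after baseline assessments have been completed") is repeated in the baseline procedures of Protocol 8.2: "Product shipment (only after baseline assessments have been completed". Protocol 6.2 has shipment tracked and asks subjects to confirm in the app both receipt and first use. No passage re-times the visits from first use.

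**The wording about use.** One exploratory objective (Protocol synopsis, Protocol Table 3-1 and SAP 3.2.2) concerns "DH sufferers following 24 weeks use of the sensitivity toothpaste". Protocol 9.3.2 asks for the score that best "describes their satisfaction with the treatment after 24 weeks of use". The synopsis states the aim as change "following the use of anti-sensitivity toothpaste for 24 weeks", and Protocol 4.1 says of subjects: "They will be asked to use it for 24 weeks, following the commercial tube instructions".

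**The outputs.** Protocol 12.4.6.1 and SAP 4.3.4 plan yes/no summaries of schedule completion and of use according to instructions, and a count of tubes remaining. Neither document plans a summary of time from baseline to first use. The output shells named in SAP 6.2 are not among the documents, so a summary specified only there cannot be ruled out.

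**The concern.** A toothpaste posted after Day 0 cannot have been used for 24 weeks by Day 168. Taken literally, a Week 24 result reported in the words of that exploratory objective or of the satisfaction assessment would claim more exposure than subjects had.

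Week 4 looks more exposed. Protocol 2.2 says potassium salts generally need 14 to 28 days of use before benefit is established. A delivery lag could put the Week 4 questionnaire early in that period or before it. With no summary of days of use, a reader could not tell a small Week 4 change from short exposure.

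**Working it through.** **Inputs.** Visit days and windows are from Protocol 1.2. The onset period of 14 to 28 days is from Protocol 2.2. The supply of 12 tubes is from Protocol Table 6-1. The lag L from baseline to first use is not given anywhere; 1, 3, 7 and 14 days are assumptions.

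**Reproducing the plan's figure.** 24 weeks × 7 = 168 days from baseline, as stated.

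**Days of use.** Use at a visit = visit day − L. Relative shortfall = L / nominal visit day.

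| L (assumed) | Use at Day 168 | Shortfall | Use over Days 161–175 | Use at Day 28 | Shortfall | Use at Day 21 |
|---|---|---|---|---|---|---|
| 1 | 167 (23.9 weeks) | 0.6% | 160–174 | 27 | 3.6% | 20 |
| 3 | 165 (23.6 weeks) | 1.8% | 158–172 | 25 | 10.7% | 18 |
| 7 | 161 (23.0 weeks) | 4.2% | 154–168 | 21 | 25.0% | 14 |
| 14 | 154 (22.0 weeks) | 8.3% | 147–161 | 14 | 50.0% | 7 |

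**Week 24.** A full 168 days of use is possible within the window when 175 − L ≥ 168, that is, when L ≤ 7. The window alone lets two on-schedule subjects differ by 175 − 161 = 14 days, as much as the longest lag assumed here.

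**Week 4.** Use is at or below 14 days at nominal Day 28 only if L ≥ 14, and at the early edge (Day 21) only if L ≥ 7. Two passages limit what this means:

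- Protocol 4.2 justifies the timepoints by published sponsor data in which DHEQ total score changed significantly after at least 8 weeks, and the slowest domain after at least 12. A small Week 4 change is expected with or without a lag.
- Protocol 12.3 and SAP 4.3.2 admit intermittent and daily users of sensitivity toothpaste. For them the first study tube need not be the start of exposure, so the onset comparison fits non-users best.

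**Questionnaires before any use.** The modified intent-to-treat rule needs one dose and one post-baseline DHEQ, in no stated order. For a Week 4 form to precede first use, L would have to exceed 21 days at the early edge or 28 days at the nominal visit, both beyond the assumed range.

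**Tube counts.** If 12 tubes cover the study period, one lasts on average at least 168 / 12 = 14 days. A lag of 3, 7 or 14 days then leaves at most 3/14 = 0.2, 7/14 = 0.5 or 14/14 = 1.0 extra tube. The SAP's categories (2 or fewer, 3 to 6, more than 6) cannot show that, but they are meant to describe compliance, not start date.

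**What the planned analyses estimate.** The primary objective is worded as a 24-week period, and the models compare each post-baseline timepoint with baseline. Both use the baseline clock throughout, so the lag introduces no error into them.

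**The case for a change.** The strongest case for a change is that it would cost little: reword a few lines and add one table of days from baseline to first use. The timing of first use is needed anyway, because Protocol 10.4 uses it to separate medical history from adverse events. Comparisons with baseline at Week 4 are planned for both DHEQ and pain, overall and by subgroup, and the DHEQ rationale in Protocol 4.2 does not cover the pain scale. The same rationale puts global oral health at no earlier than 24 weeks, so for that item even a small Week 24 shortfall is not plainly irrelevant.

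Much of this stands. The wording about use is loose, and a short description of the lag would help a reader, mainly for Week 4 results in non-users. But it does not show that following the plan gives a wrong result. Every planned plot and model would stay as it is, and no objective makes a claim specific to Week 4. If benefit builds with use, the lag works against showing improvement, not for it. Shipping after baseline is also a fair trade: it guarantees a baseline untouched by the product, at the price of a lag that is part of ordinary use of a posted product. The striking figures, half the exposure at Week 4 or only 7 days of use, need a 14-day lag, and the second also needs a visit on the earliest permitted day. Nothing in the documents supports a lag of that length.

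**Conclusion.** No change to the plan follows. Time on product at nominal Day 168 is under 24 weeks for any positive lag, so the phrases about 24 weeks of use are best read as 24 weeks after baseline. With an assumed lag of 3 to 14 days the gap is 3 to 14 days in 168 (1.8% to 8.3%), and a lag of up to 7 days falls within the visit window. At Week 4 the same lags leave 25 to 14 days of use. That calls for care in reading the Week 4 results but does not alter any analysis.

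The remaining gap is one that analysts fill sensibly: label time axes as weeks since baseline, and describe the first-use confirmations alongside compliance. The conclusion rests on the assumed lags and on first-use timing being retrievable; Protocol 6.2 does not say that a date is stored, though the adverse-event rule in 10.4 depends on it. Lags beyond about three weeks would make the Week 4 results hard to interpret, but the documents give no reason to expect them.
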